If the change represents more than minimal risk to subjects, it must be reviewed and approved by the IRB at a convened meeting. For a modification to be considered more than minimal risk, the proposed change would increase the risk of discomfort or decrease benefit. The IRB must review and approve the proposed change at a convened meeting before the change can be implemented unless the change is necessary to eliminate an immediate hazard to the research participants. In the case of a change implemented to eliminate an immediate hazard to participants, the IRB will review the change to determine that it is consistent with ensuring the participant's continued welfare. Examples: Convened Board Increase in target enrollment for investigator initiated research or potential Phase I research Expanding inclusion or removing exclusion criteria where the new population may be at increased risk Revised risk information with active participants Minor risk revisions that may affect a subject's willingness to continue to participate Expedited Review Increase in target enrollment at Penn where overall enrollment target is not exceeded or potentially sponsored research Expanding inclusion or removing exclusion where the new population has the same expected risk as the previous, based on similarities of condition Revised risk information with subjects in long-term follow-up Minor risk revisions with no subjects enrolled to date Expedited Review

Modification Summary

Please describe any required modification to the protocol. If you are using this form to submit an exception or report a deviation, enter 'N/A' in the box below.

Adding study staff. [name]'s CITI training certificates are attached to protocol resubmission.

Risk / Benefit

Does this amendment alter the Risk/Benefit profile of the study?

No

Change in Consent

Has there been a change in the consent documents?

No

If YES, please choose from the options below regarding re-consenting

Deviations

Are you reporting a deviation to this protocol?*

No

Exceptions

Are you reporting an exception to this protocol?*

No

Protocol Details

Resubmission*

Yes

Hospital Sites

Will any research activities and/or services be conducted at a Penn Medicine affiliated hospital site? Yes

Active Hospital Sites

Pennsylvania Hospital (PAH) ***Primary***

Study Personnel

Principal Investigator

Name:	[name]
Dept / School / Div:	4333 - OB-Obstetrics and Gynecology
Campus Address	
Mail Code	
Address:	

I have reviewed the *Financial Disclosure and Presumptively Prohibited Conflicts for Faculty Participating in Clinical Trials* and the *Financial Disclosure Policy for Research and Sponsored Projects* with all persons who are responsible for the design, conduct, or reporting of this research; and all required Disclosures have been attached to this application.

Yes

Biomedical Research

Clinical Trial*

Is this a clinical trial?

Yes

If Yes, please be aware that for each clinical trial conducted or supported by a Federal department or agency, one IRB-approved informed consent form used to enroll subjects must be posted by the awardee or the Federal department or agency component conducting the trial on a publicly available Federal Web site that will be established as a repository for such informed consent forms.

Investigator Initiated Trial*

Is this an investigator initiated trial?

No

Drugs or Devices*

Does this research study involve Drugs or Devices?

No

IND Exemption

For studies that fall under an IND exemption, please provide the number below

For studies including IND or IDE's, please provide the number(s) below

IDE Review*

NOTE: For research involving investigational devices, you are required to review the guidance on Managing Research Device Inventory. Consult the Penn Manual for Clinical Research: [https://www.med.upenn.edu/pennmanual/secure/investigational-product-management-at-sites-not-usinginvestigational-drug-services-\(ids\).html](https://www.med.upenn.edu/pennmanual/secure/investigational-product-management-at-sites-not-usinginvestigational-drug-services-(ids).html) Please check the box Yes if you have reviewed the guidance.

No

Research Device Management*

Please indicate how research device(s) will be managed.

Not Applicable (no investigational devices)

Drug, Herbal Product or Other Chemical Element Management *

Please indicate how drugs, herbal products or other chemical entities will be managed. Not

Applicable (no drugs, herbal products or other chemical entities)

Radiation Exposure*

Are research subjects receiving any radiation exposure (e.g. X-rays, CT, Fluoroscopy, DEXA, pQCT, FDG, Tc-99m, etc.) that they would not receive if they were not enrolled in this protocol?

No

Gene Transfer*

Does this research involve gene transfer (including all vectors) to human subjects?

No

Human Source Material*

Does this research include collection or use of human source material (i.e., human blood, blood products, tissues or body fluids)?

No

CACTIS and CT Studies*

Does the research involve Center for Advanced Computed Tomography Imaging Services (CACTIS) and CT studies that research subjects would not receive if they were not part of this protocol?

No

CAMRIS and MRI Studies*

Does the research involve Center for Advanced Magnetic Resonance Imaging and Spectroscopy (CAMRIS) and MRI studies that research subjects would not receive if they were not part of this protocol?

No

Investigational Agent or Device within the Operating Room*

Does the research project involve the use of an investigational agent or device within the Operating Room?

No

Cancer Related research not being conducted by an NCI cooperative group*

Does this protocol involve cancer-related studies in any of the following categories?

No

Processing of Materials*

Will the research involve processing (such as over encapsulating, or compounding)?

No

In-House Manufacturing of Materials*

Will the research involve processing (such as over encapsulating, or compounding)?

No

Medical Information Disclosure*

Does the research proposal involve the use and disclosure of research subject's medical information for research purposes? Yes

If the answer is YES, indicate which items is is provided with this submission:

Request for HIPAA Waiver of Authorization

CTR C Resources*

Does the research involve CTRC resources?

No

Pathology and Laboratory Medicine Resources*

Will samples be collected by hospital phlebotomy and/or processed or analyzed by any of the clinical laboratories of the University of Pennsylvania Health System?

No

Research Involves Apheresis, Cell Collection, and/or Blood Product Collection*

Does this research involve collection of blood products in the Penn Donor Center and/or the use of apheresis for treatment or collection of cells or other blood components?

No

Research involving blood transfusion or drug infusions*

Will your research involve blood transfusion or infusion of study drug in 3 Ravdin Apheresis Unit for research purposes?

No

Trial in Radiation Oncology

Is this research a prospective trial being done in Radiation Oncology, and if so, has this protocol been approved by the Radiation Oncology Protocol committee?

N/A

Study in Radiation Oncology

Is this research a retrospective study being done in Radiation Oncology, and if so, has this project been reviewed by the Radiation Oncology Clinical Research Group?

N/A

Use of UPHS services*

Does your study require the use of University of Pennsylvania Health System (UPHS) services, tests or procedures*, whether considered routine care or strictly for research purposes?

No

Primary Focus*

Clinical Trial (prospectively assigning subjects to health-related interventions to evaluate outcomes)

Protocol Interventions

Sociobehavioral (i.e. cognitive or behavioral therapy)

Drug

Device - therapeutic

Device - diagnostic (assessing a device for sensitivity or specificity in disease diagnosis)

Surgical

Diagnostic test/procedure (research-related diagnostic test or procedure)

Obtaining human tissue for basic research or biospecimen bank x

Survey instrument

None of the above

The following documents are currently attached to this item:

There are no documents attached for this item.

Sponsors

Business Administrator

Name:	[name]
Dept / School / Div:	4333 - OB-Obstetrics and Gynecology
[contact]
Fax:	-
Pager:	
Email:	[contact]

Department budget code

400 - 400 - 2 - 014001 - xxxx - 2813 - 0940

Funding Sponsors

Funding sponsors billing address

If you have selected a commercial or industry sponsor, please provide the appropriate address and contact information for the Sponsor for the purposes of billing for IRB review fees (initial review, continuing review and convened modification fees apply here). If the Sponsor is not industry/ commercial, this information is not necessary to provide with your application.

N/A

Funding sponsors gift

Is this research being funded by a philanthropic gift?

No

Regulatory Sponsor

IND Sponsor

none

400 - 400 - 2 - 014001 - xxxx - 2813 - 0940

Industry Sponsor

None

Project Funding*

Is this project funded by or associated with a grant or contract?

No

Sponsor Funding

Is this study funded by an industry sponsor?

Status of contract

The following documents are currently attached to this item:

There are no documents attached for this item.

Multi-Center Research

Penn as lead

1. Is this a multi-center study where Penn is serving as the Lead Site or the Penn PI is serving as the Lead Investigator?

No

Management of Information for Multi-Center Research

Penn irb of record

2. Is this a multi-center study where the Penn IRB will be asked to serve as the IRB of Record for other external study sites?

No

Other Sites

No other sites

Protocol

Abstract

Hypertensive disorders of pregnancy (HDP) are stress tests which may identify women at high risk of future cardiovascular disease (CVD), the leading cause of death among women. Given the public health impact of HDP and CVD, there is a compelling need to identify scalable interventions to improve preventative care among women who have risk identified during pregnancy. We will examine the effects of delivering electronic prompts to obstetric care providers (nudge) on transitions of care in the postpartum period. We will conduct a pilot randomized trial to evaluate whether this nudge intervention will improve postpartum counseling and lead to greater follow-up with preventative care providers among women with HDP. **Objectives**

Overall objectives

The objective of the study is to evaluate the effect of a hospital-wide initiative using electronic prompts to encourage physicians to transition care for women with HDP to continuity care providers in accordance with national society guidelines.

Primary outcome variable(s)

The primary outcome measure is documentation of counseling about transitioning care to a continuity care provider (primary care or cardiology) at the postpartum visit.

Secondary outcome variable(s)

Secondary outcomes include 1. Electronic prompts opened by obstetric care providers within 1 week of receipt. 2. Documentation of CVD risk at the postpartum visit. 3. Use of scripted dot phrases (available in Epic) for counseling on transitions of care and CVD risk in the postpartum note. 4. Attendance at a primary care or cardiology visit for preventative care within 6 months of delivery.

Background

Women with HDP need ongoing care in the postpartum and inter-pregnancy period. HDP, including PEC and gestational hypertension (GHTN), complicate up to 10% of all pregnancies and are associated with immediate and long-term cardiovascular morbidity and mortality.¹ HDP increase lifelong risk for chronic hypertension, diabetes, ischemic heart disease, stroke, and heart failure.²⁻⁵ Black women have a higher incidence of HDP and have a disproportionately higher morbidity and mortality compared to non-black women.^{6,7} ACOG and the American Heart Association (AHA) emphasize the postpartum period as an important opportunity to identify and intervene upon women at high-risk for future cardiovascular disease (CVD).^{8,9} However, current postpartum practices inadequately address transitions of care for women with

HDP. A significant proportion of women with HDP do not see a preventative care provider (primary care, cardiology) in the months after delivery.¹⁰⁻¹² Black women are particularly vulnerable to being lost to follow-up after complicated pregnancy.^{10,11} The HSM program is an innovative, patient-centered program that monitors postpartum blood pressure remotely using a text-based interface. It is supported by the Way to Health platform. HSM improves blood pressure management in the two weeks after delivery and eliminates racial disparities in blood pressure ascertainment during that time.^{13,14} However, enrollment in HSM did not improve follow-up in the year after delivery, with less than 1/3 of women having a preventative care visit.¹⁵ Poor follow-up is likely multifactorial, but may be driven by inadequate patient counseling in the postpartum period. Among women enrolled in HSM, only 21% of women were counseled on follow-up with primary care and only 4% were counseled on CVD risk at their postpartum visits based on chart review.¹⁶ Nudges are effective for changing medical decision-making and improving clinical outcomes. Nudges utilize concepts from behavioral economics to subtly change the decision-making environment to facilitate evidence-based care and can be delivered to patients, providers, or both.¹⁷ Examples of nudges include electronic prompts to order cancer screening and electronic defaults that guide ordering practices.¹⁸ Nudges are low cost, scalable using Electronic Medical Record (EMR) systems, and improve rates of preventative services including influenza vaccination, referral to mammography, and statin prescription for CVD prevention.¹⁹⁻²²

References:

1. American College of Obstetricians and Gynecologists; Task Force on Hypertension in Pregnancy. Executive summary: hypertension in pregnancy. *Obstet Gynecol* 2013;122:1122-31.

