This study will be a randomized, controlled superiority trial to evaluate a hospital-wide initiative to improve counseling for postpartum women who experienced HDP during their pregnancy or in the immediate postpartum period. Hypotheses: 1. We hypothesize that the prompt will increase the proportion of women counseled on transitioning care to a primary care provider or cardiologist after pregnancy (primary outcome). 2. We hypothesize that the provider nudge will increase the proportion of women attending a preventative care visit within 6 months of delivery as assessed by chart review and patient surveys. The HSM daily log generated through the Way to Health platform will be used to generate lists of patients who eligible for the study. For each eligible woman, the date of and obstetric care provider for her postpartum visit will be recorded within 3 weeks of delivery. Patients will then be randomly assigned to a control group with no intervention (usual care through HSM) or the intervention group (physician nudge) using simple 1:1 randomization through the Way to Health Platform. If a woman is randomized to the intervention arm, her obstetric care provider for her postpartum visit will receive a staff message in Epic (Penn Chart) that his/her patient has an upcoming postpartum visit. The message will be sent 1 week before the scheduled visit. The message will have patient-specific information including hypertensive diagnosis, blood pressure medication(s), gestational diabetes diagnosis, and primary care provider as listed in the Epic banner. The message will also have dot phrases for recommended counseling and contact information for UPHS primary care and cardiology providers. There will be a dot phrase recommending follow-up with primary care or cardiology; counseling on risk of future CVD; and recommending aspirin in a future pregnancy. A web-based survey will be distributed to all women in the study 6 months after delivery through the Way to Health platform. The survey will assess attendance at a preventative care visit, social determinants of health, health status, and insurance status after delivery. Demographic characteristics, medical and obstetric history, hypertensive disorder, laboratory test results (platelet count, creatinine, liver function tests, urine protein, total cholesterol, triglycerides, LDL-C, HDL-C, glucose, hemoglobin A1c), blood pressure measurements, height, weight, and office visits within 6 months of delivery will be abstracted from the EMR. We will perform detailed abstraction of counseling at the postpartum visit and additional office visits within 6 months of delivery focusing on 1) health maintenance 2) hypertension, or 3) cardiovascular risk reduction. Two reviewers will assess counseling at each visit. We will obtain data on obstetric care providers including level (resident physician, attending physician, nurse practitioner, physician assistant, or certified nurse midwife), gender, and years in practice from publicly available databases or websites online.

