Sample size calculations were based on the assumption that 21% of patients in usual care and 40% of patients receiving a provider nudge would have documentation about transitioning care. A sample size of 222 patients (randomized 1:1) would provide 80% power to detect this difference assuming 20% of patients will not attend their postpartum visit. Approximately 100 women are enrolled in HSM each month at Pennsylvania Hospital. We anticipate that over 90% of those women receive prenatal care at a UPHS practice (n=90 per month), and at least 80% will attend a postpartum visit (n=72). We thus anticipate that 222 women could be enrolled in 3-4 months, allowing for 6-month follow-up during the grant period.

Key inclusion criteria

1. At least 18 years old. 2. Have a diagnosis of HDP during delivery admission or have a diagnosis made at time of evaluation in the Perinatal Evaluation and Treatment Unit after discharge from the delivery admission. HDP diagnoses are based on criteria from the American College of Obstetricians and Gynecologists (ACOG). 3. Enrolled in HSM at Pennsylvania Hospital. 4. Have a postpartum visit with a UPHS provider scheduled 4-12 weeks after delivery.

Key exclusion criteria

1. Women diagnosed with chronic hypertension (CHTN) without superimposed pre-eclampsia (PEC).

Vulnerable Populations

Children Form

Pregnant women (if the study procedures may affect the condition of the pregnant woman or fetus) Form

Fetuses and/or Neonates Form

Prisoners Form

Other x None of the above populations are included in the research study

The following documents are currently attached to this item:

There are no documents attached for this item.

Populations vulnerable to undue influence or coercion

This is a hospital-wide initiative which will equally include all postpartum women in HSM who do not meet exclusion criteria.

Subject recruitment

The HSM daily log generated through the Way to Health platform will be used to generate lists of patients who eligible for the study. For each eligible woman, the date of and obstetric care provider for her postpartum visit will be recorded within 3 weeks of delivery.

Will the recruitment plan propose to use any Penn media services (communications, marketing, etc.) for outreach via social media avenues (examples include: Facebook, Twitter, blogging, texting, etc.) or does the study team plan to directly use social media to recruit for the research?

No

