A flowsheet of patient participation is attached. Subjects will be identified through the HSM daily log. A waiver of informed consent is requested for the intervention portion of this study. At 30 days after discharge, all participants, regardless of study arm will receive the following message "Hello from Heart Safe Motherhood! We hope you are doing well. Dont forget to follow-up with your primary or heart doctor in the next 2-4 weeks. If you were given an appointment, make sure to keep it. If you want to make an appointment with a heart doctor focused on women's health, call [contact]. Have a great day!" At 6 months postpartum, women will receive a secure text message through the Way To Health platform. "We are trying to understand how women with high blood pressure or preeclampsia stay healthy after delivery. Respond yes if you are willing to complete a survey. You will receive \$5 for participating." If she responds yes, she will receive a survey link integrated with Way To Health. Patient information will be obtained from the electronic medical record including demographic characteristics, medical and obstetric history, hypertensive disorder, laboratory test results (platelet count, creatinine, liver function tests, urine protein, total cholesterol, triglycerides, LDL-C, HDL-C, glucose, hemoglobin A1c), blood pressure measurements, height, weight, and office visits within 6 months of delivery. We will perform detailed abstraction of counseling at the postpartum visit and additional office visits within 6 months of delivery focusing on 1) health maintenance 2) hypertension, or 3) cardiovascular risk reduction. Two reviewers will assess counseling at each visit (from the discharge summary and after visit summary). We will obtain data on obstetric care providers including level (resident physician, attending physician, nurse practitioner, physician assistant, or certified nurse midwife), gender, and years in practice from publicly available databases or websites online.

The following documents are currently attached to this item:

There are no documents attached for this item.

Deception

Does your project use deception?

No

International Research

Are you conducting research outside of the United States?

No

Analysis Plan

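### The 6-month attendance outcome counts visits made before the nudge can act, which dilutes the relative risk for hypothesis 2; a pre-specified landmark analysis is a cheap improvement

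*Combined protocol and SAP*

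**What the plan says.** The outcome is listed under Secondary outcome variable(s) and repeated in the Analysis Plan as "Attendance at a primary care or cardiology visit for preventative care within 6 months of delivery". Hypothesis 2 in the Design section is that "the provider nudge will increase the proportion of women attending a preventative care visit within 6 months of delivery", assessed from charts and patient surveys. None of these places gives an earliest date or excludes earlier visits. Chart abstraction covers "additional office visits within 6 months of delivery focusing on 1) health maintenance 2) hypertension, or 3) cardiovascular risk reduction", which selects visits by focus and not by date.

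The timing of the intervention is explicit. Entry requires that women "Have a postpartum visit with a UPHS provider scheduled 4-12 weeks after delivery". In the nudge arm the obstetric provider, not the patient, is contacted: "The message will be sent 1 week before the scheduled visit". Before assignment, "the date of and obstetric care provider for her postpartum visit will be recorded within 3 weeks of delivery", and this is done for every eligible woman.

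Under Procedures, women in both arms also get a text 30 days after discharge: "Dont forget to follow-up with your primary or heart doctor in the next 2-4 weeks". The Analysis Plan reports proportions and relative risks with 95% confidence intervals, by intention to treat, at two-sided alpha 0.05.

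**The concern.** The outcome window opens at delivery, but the intervention starts weeks later. A woman who sees a primary care doctor or cardiologist for preventive care in week 2 is already a success, whichever arm she is in, and nothing the nudge does can change her result. Such women add the same expected amount to both proportions. The relative risk for hypothesis 2 therefore moves towards 1, and the test carries variance from events that say nothing about the nudge.

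The 30-day text makes some early attendance plausible. If discharge is 2-4 days after delivery (an assumption), the text points to days 46-62, or weeks 6.6-8.9. That precedes the counselling for visits booked from week 9, and precedes even the message for visits booked from week 10.

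At stake is how sensitively the trial tests one of its two numbered hypotheses.

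**Working it through.** **Plan's own figure.** The Accrual section gives 222 women for 21% vs 40%, 80% power, 20% not attending the postpartum visit. With unpooled variance: (1.960 + 0.842)² × (0.21×0.79 + 0.40×0.60) / 0.19² = 88.25 per arm, and 2 × 88.25 / 0.8 = 220.6. The figure reproduces closely, but it concerns counselling only. No power, control rate or target effect is stated for attendance.

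**Window.** Six months is about 26 weeks. The time before counselling is 4/26 = 15% to 12/26 = 46%; before the message, 3/26 = 12% to 11/26 = 42%. These are shares of calendar time, not of visits.

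**How large an effect is plausible.** If the nudge works by adding counselled women, the sample-size assumptions imply at most (40 − 21) × 0.8 = 15.2 extra women counselled per 100 randomised. If half of them attend because of it, the gain is 7.6 points; if about a third, 5.0 points.

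**Model.** Inputs:
- Control attendance by 6 months P = 33%, a ceiling, since the Background gives less than one third over a year.
- n = 222/2 = 111 per arm.
- Share of control attenders seen before the message-due date s = 25% or 50% (assumed; not in the documents).
- Absolute gain d per woman randomised.

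Let e = sP.
- As written: P vs P + d, with RR = (P + d)/P.
- Landmark: h = (P − e)/(1 − e) vs h + d/(1 − e), with 111(1 − e) women per arm.
- Power, with p0 and p1 the two proportions and p̄ their mean: Φ{[|p1 − p0| − 1.96√(2p̄(1 − p̄)/n)] / √[(p0(1 − p0) + p1(1 − p1))/n]}.

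Example, s = 50%, d = 7.6 points: e = 0.165; h = 0.165/0.835 = 0.198; nudge arm 0.198 + 0.076/0.835 = 0.289; n = 92.7. The RR is 0.289/0.198 = 1.46, against 0.406/0.33 = 1.23 as written.

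| s | d (points) | RR, power as written | RR, power with landmark | Gain (points) |
|---|---|---|---|---|
| 25% | 5.0 | 1.15, 11.8% | 1.20, 13.3% | 1.5 |
| 50% | 5.0 | 1.15, 11.8% | 1.30, 16.1% | 4.3 |
| 25% | 7.6 | 1.23, 21.5% | 1.31, 24.6% | 3.1 |
| 50% | 7.6 | 1.23, 21.5% | 1.46, 30.2% | 8.7 |
| 50% | 12.4 | 1.38, 47% | 1.75, 62% | 15 |
| 25% | 18.6 | 1.56, 80% | 1.75, 85% | 5 |

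The last two rows assume that the nudge multiplies later attendance by 1.75. The 12.4-point row needs 12.4/15.2 = 82% of newly counselled women to attend because of the counselling. The 18.6-point row exceeds the 15.2-point ceiling.

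At P = 25% and the same 5.0-7.6 point effects, power goes from 13.0% to 14.8-18.2% and from 23.8% to 27.6-34.2%, a gain of 1.8 to 10.4 points. If s = 0, the two analyses coincide.

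**The case against.** The strongest reply is that the delivery-based proportion is a legitimate policy outcome: whether a woman reached continuity care within 6 months. Early attenders are real successes, and the plan hypothesises exactly this quantity. That stands, and it is why the delivery-based result should be kept. The number of extra attenders, and so the difference in proportions over all randomised women, is the same under either definition. Because the plan reports proportions as well as relative risks, the absolute gain stays visible.

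A reader might infer that early visits bias the comparison or raise the false-positive rate. They do neither: the arms are treated alike until the message is due. A reader might also infer that a null on hypothesis 2 would be explained by the window. The working does not support that: at effects of 5.0-7.6 points power is low with or without the landmark, so sample size would be the main explanation.

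Three further points stand in part:
- The share of early visits is unknown, and the restriction to preventive care may already remove some early blood-pressure checks.
- The Design section also uses patient surveys, and no visit date is mentioned among the items they collect. A visit known only from the survey might not be placeable before or after the landmark.
- The landmark removes some randomised women and does not remove every text-prompted visit. It suits an added analysis, not a replacement for the intention-to-treat result.

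On the other side, the 15.2-point ceiling is not strict: a prompt could also improve the counselling of women who would have been counselled anyway.

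**Conclusion.** The point holds as a cheap improvement to a secondary outcome. Visits before about weeks 3-11 (message) or 4-12 (counselling) count towards hypothesis 2 although the nudge cannot have caused them, and they dilute the planned relative risk. The likely cost is small: 1.5 to 8.7 points of power at 33% control attendance, 25-50% of attenders seen early and absolute effects of 5.0-7.6 points. Much larger losses appear only for effects near what the plan's own counselling gain could produce. All sizes rest on an assumed early share, an assumed control rate and the simple model above. The direction of the effect on the relative risk needs only that some attenders are seen early and that the nudge has a positive effect.

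**What to change.** Before outcome data are examined, add to the outcome definition and the Analysis Plan, for hypothesis 2:

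- **Start date.** The postpartum visit date as recorded before randomisation, minus 7 days, in both arms, and not updated if the visit is rescheduled. Using the attended visit instead would drop the assumed 20% who do not come.
- **Analysis.** First preventive primary care or cardiology visit from that date to 6 months after delivery, among women with no such visit before it. The restriction depends only on events before the arms diverge, so it preserves the randomised comparison, provided that early visits are ascertained equally in both arms.
- **Alongside it.** The delivery-based proportion in all randomised women, as the full intention-to-treat result.
- **Data.** Base the landmark analysis on visits dated in the medical record. Add a visit-date item to the 6-month survey, or treat undated survey-only visits in a sensitivity analysis.

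The cost is a few sentences, possibly one survey item, and a slightly smaller denominator (in the example, 92.7 instead of 111 per arm). The result is also less directly comparable with earlier figures counted from delivery. Office visits over the 6 months are already being abstracted.
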